The clinical study as detailed within this research protocol (Version 3.0 dated 02.11.2016), or any subsequent amendments will be conducted in accordance with the Research Governance Framework for Health & Social Care (2005), the World Medical Association Declaration of Helsinki (1996) and the current applicable regulatory requirements and any subsequent amendments of the appropriate regulations.

Principal Investigator	Site	Signature and Date				
Name						
[name]	Queen Margaret					
Co-chief Investigator	University					
[name]	King's College Hospital					
[name]	Salford Royal Hospital					
[name]	Glasgow Royal Infirmary					
[name]	Birmingham Heartlands					
	Hospital					
[name]	Royal Derby Hospital					
[name]	Betsi Cadwaladr					
	University Health Board					

STUDY SUMMARY/SYNOPSIS

Does intra-dialytic exercise improve health-related quality of life in maintenance haemodialysis patients?

TITLE	Clinical value and cost-effectiveness of intra-dialytic exercise for the improvement of quality of life in stage 5 chronic kidney disease patients receiving maintenance haemodialysis
SHORT TITLE	PEDAL Study
Protocol Version	V2.0
Number and Date	17 July 2015
Methodology	Pragmatic, single-blind randomised controlled trial
Phase	IV
Study Duration	48 months
Study Centre	Multi-centre
Objectives	To determine, in comparison to usual care, whether usual care augmented by intra-dialytic exercise training improves health-related quality of life in stage 5 CKD patients receiving maintenance haemodialysis renal replacement therapy
Number of Subjects/Patients	380 participants
Diagnosis and Main Inclusion Criteria	Evaluation of the clinical value and cost-effectiveness of usual care augmented intra-dialytic exercise training in the management of 380 stage 5 chronic kidney disease patients receiving maintenance haemodialysis renal replacement therapy
Duration of intervention	9 months
Reference therapy	Usual care maintenance haemodialysis renal replacement therapy
Methodology and Analysis	Primary analysis will be ANCOVA comparison of 6 month outcomes, adjusted for baseline differences. Secondary analyses will be multivariate repeated measures analysis, adjusted for baseline differences

Glossary of Terms and Abbreviations

AE Adverse Event
CI Chief Investigator

CKD Chronic Kidney Disease

CRO Contract Research Organisation

CRP C-Reactive Protein

DASI Duke Activity Status Index

DSMC Data Safety Monitoring Committee eCRF Electronic Case Report Form

1.1 Background

PEDAL is a pragmatic, multi-centre single-blind randomised controlled trial (RCT) designed to evaluate the clinical value and cost-effectiveness of intra-dialytic exercise training as a means to improve the health-related quality of life of people with stage 5 chronic kidney disease who are receiving maintenance haemodialysis renal replacement therapy.

We intend to recruit 380 prevalent adult renal outpatients (aged 18+), from those undergoing in-centre (hospital unit, satellite unit) renal replacement therapy via maintenance haemodialysis. Patients will be eligible if they have been dialysing for more than three months and are naive to intra-dialytic exercise. Eligible and consenting patients will then be randomly allocated to one of two treatment arms: usual care maintenance haemodialysis renal replacement therapy (UCHD) or usual care augmented by intra-dialytic exercise training (EXHD).

The primary clinical outcome for the study is the change in Kidney Disease Quality of Life (KDQOL) Physical Composite Score between baseline and 6 months. Additional important secondary outcomes will include change in peak aerobic capacity, physical fitness, arterial stiffness (pulse wave velocity) and blood pressure, other quality of life and symptom burden assessments (KDQOL-Mental Composite Score, EQ5D, , habitual physical activity levels and cost effectiveness. Participants will receive 9 months exposure to either their usual care therapy or the intra-dialytic exercise training augmented usual care. Outcomes of the intervention will be measured at entry to the study (0 months) and again after 6, 9 and 15 months.

The incidence of new patients accepted for renal replacement therapy in the UK has almost doubled in 10 years from 60 patients per million population (pmp) to 110pmp (1). Diabetes remains the single most common cause of the gradual loss of kidney function and in combination with cardiovascular disease (CVD), is responsible for the 10-30 times greater mortality rates of HD patients compared to the general population (2). Improved dialysis techniques and management of co-existing disease, have made HD more tolerable and many new patients can anticipate a longer life expectancy (3), although not always with a good quality of life. In part, this may reflect the increased age profile of incident patients with a median age of 65 years and the associated presence of the clinical syndrome of frailty (4). This syndrome is characterised by persistent fatigue, weight loss, muscle weakness, severe functional limitations and low physical activity (PA) levels many of which often deteriorate further with the initiation of HD (5). Both physical inactivity and impaired physical function are strongly associated with increased morbidity, mortality and reduced quality of life (QOL) in HD patients (6,7,8). QOL is also independently associated with mortality in HD patients with SF36QOL-Physical Composite scores (PCS) of less than 25 associated with a 93% increased risk of death and a 56% increased risk of hospitalisation, whilst a 10-point decrease in the PCS translated into a 25% increased risk of death within 2 years (8). Conversely, a 1-point increase in the PCS was associated with a 3.5% improvement in the odds of death (9). Resultantly, interventions designed to increase PA and reduce sedentary behaviour in HD patients might reduce CVD risk, improve physical functioning, reduce fatigue and in turn possibly lead to improved QOL. Evidence from three (10,11,12) systematic reviews indicates that a range of exercise training interventions show potential to

King's College Hospital

NHS Foundation Trust

improve exercise capacity and some functional limitations in people with chronic kidney disease. The greatest effects were reported after 6 months of exercise and were associated with both supervised and higher intensities of exercise. However, most of the studies reviewed were small trials, many of which were not methodologically robust, and also included non-intra-dialytic interventions in the evidence synthesis. Few of the reviewed studies were appropriately powered to detect QOL outcomes and none included a cost effectiveness analysis. Older, comorbid individuals, with the additional burden and consequences of the HD process, represent a classic example of a frail population. Compared to adults without CKD, self-reported ability to participate in activities of daily living, such as climbing steps, walking short distances without stopping and daily self-care tasks, is extremely low in HD patients regardless of age (4,13,14). Within 1 year of initiating HD, frail patients were more likely to die or be hospitalised compared to non-frail patients (4,13) and only 5% of elderly HD patients (mean age: 75 years) were fully independent (14). In the HD population physical function and PA are strongly associated with overall quality of life, morbidity and mortality (6,7,8,9,15). Sietsema et al.(6) observed that exercise capacity was predictive of outcome in 175 ambulatory HD patients. Patients with a peak aerobic capacity above the median threshold of 17.5 mL/kg/min had a statistically lower rate of death during the 3.5 years follow-up period. Moreover, exercise capacity remained the strongest predictor of survival over the 3.5-year follow-up, even when corrected for other contributing variables. Analysis of data from the USRDS Dialysis Morbidity and Mortality Study indicated that patients classified as sedentary at study initiation showed a 62% greater risk of mortality over 1 year compared with non-sedentary patients even after adjustment for other variables associated with survival in this group (15). Recent systematic review evidence (11) suggests that, when compared to standard care, exercise interventions during dialysis can statistically improve physical fitness (peak aerobic capacity) by about 18%, or at least appear to limit the potential for the relentless deterioration of physical and psychosocial function observed across all stages of CKD. The Dialysis Outcomes and Practice Patterns study (DOPPS) observed that patients who exercised during dialysis more than twice a week had significantly better scores in the mental and physical components of the KDQoL-SF, physical function and quality of sleep, compared to patients who exercised less frequently (16). Regularly exercising patients were also 33% less likely to be hospitalised due to fractures. Interestingly, a 9% lower mortality risk was observed for each 10% increment in the number of patients exercising within a unit whilst mortality risk was reduced by 31% as patient exercise frequency increased from 1 to 6 or more times per week.

Fatiguability, defined as an overwhelming, debilitating, and sustained sense of exhaustion that decreases one's ability to carry out daily activities, is another prevalent and severe symptom experienced by patients in stage 5 CKD (17). The burden of this symptom is substantial, with patients reporting a severity of 3.1 units on a 1 (not at all bothersome) to 5 (bothers very much) scale (17). As a further indicator of the importance of this symptom, 94% of patients would accept longer haemodialysis if fatigue was reduced (18). Fatigue is also associated with CKD patient QOL and mortality (17,19). Furthermore, fatigue is a barrier to participating in physical activity (20). In CKD patients a recent Cochrane review discursively suggested that exercise can reduce feelings of fatigue (11). However, a meta-analysis on the influence on fatigue was not possible due to insufficient numbers of participants and moderate to severe risk of study bias. In other fatigued populations including chronic fatigue syndrome, exercise can reduce fatigue symptoms (21,22). Implementing an exercise programme is also likely to have a statistically significant

and clinically important improvement to patient reported fatigue, which then may encourage patients to sustain more physically active life styles in the longer term (20).

1.2 Rationale and Risks/Benefits

The rationale for intra-dialytic exercise is both intuitively and pragmatically appealing as the environment of unit-based HD provides an ideal platform for the implementation and potential sustainability of exercise rehabilitation programmes for, and thus the exercise behaviour of, HD patients. The pre-existing need for patients to attend thrice-weekly, 4 hour-long HD sessions, provides a practical opportunity to deliver a safely structured and supervised rehabilitation programme with an enhanced potential for participation, associated with a substantially reduced patient burden in terms of time, effort and travel costs. The importance of the patient inconvenience burden has been confirmed by a previous study that reported a lower drop out rate from intra-dialytic exercise training (17%) compared to an exercise training programme (25%) for HD patients conducted on non-dialysis days (23). Time spent on dialysis is also reported to be the most physically inactive period for HD patients (24) and thus an exercise intervention implemented during HD would directly address the important key PA guideline that recommends the reduction of prolonged periods of inactivity to the minimum (28). The K/DOQI Clinical Practice Guidelines for the management of CV disease risk factors in patients with CKD now include a separate guideline section (guideline 14) supporting physical activity promotion as an integral part of patients' care plans (25). Clear research recommendations are proposed to strengthen the evidence base on the best way to incorporate PA into the routine care of HD patients. This indicates a need for the resolution of what might, for HD patients, constitute the optimal exercise prescription for the delivery of health outcomes, including combatting frailty and reduction of cardiovascular risk. We believe that our study proposal, by addressing many of the methodological weaknesses of previous studies, will resolve some of the remaining issues around the efficacy of exercise training to deliver health-related benefits for HD patients. In addition, through the incorporation of the cost effectiveness analysis we believe that we will be in a position to offer a methodologically robust and long awaited insight in relation to an implementation strategy for long term adoption and sustainability of intra-dialytic exercise training in HD units across the UK and other countries.

Evidence explaining why this research is needed now

Recent clinical practice guidelines for Cardiovascular Disease (CVD) in CKD produced by the U.K Renal Association (26) suggest that exercise should be encouraged, and patients (including dialysis patients) should be enrolled on regular exercise programmes, exercising 3 to 5 times weekly either during dialysis or between dialysis sessions (Guideline 1.4-CVD: CVD risk factors). A major obstacle to the implementation of such exercise programmes in many UK NHS Renal Units is the lack of evidence from high quality randomised controlled trials of intra-dialytic exercise training. This is often required to justify the necessary costs of programme set-up and delivery. As a result, only a few renal units are able to provide this type of therapy resulting in an inequality of service provision that needs to be urgently addressed. A need for quality evidence remains despite the publication of the recent Cochrane Review (11) which indicated some potential for exercise training interventions in CKD patients. Most of the trials reviewed used inadequate randomisation procedures and/or failed to undertake intention-to-treat (ITT) analyses,

resulting in a moderate to high degree of bias being identified in 82% of the trials included in the meta-analysis. Taken together, these weaknesses can combine to exaggerate the impact of an intervention. There was also evidence of significant heterogeneity between trials indicating that results were not consistent across studies. This is perhaps understandable given the extremely wide remit applied by the authors of that review, covering the entire CKD disease trajectory and also many modes of exercise training, including non-intra-dialytic interventions. Only two studies using combined aerobic and muscular conditioning exercise interventions during dialysis were included and only two of the trials studied whether or not any benefits of an exercise intervention persisted beyond the intervention. Also, the vast majority of reported trials of exercise training with HD patients were underpowered to detect anything other than a massive treatment effect and none reported cost effectiveness data. Physical inactivity is a modifiable risk factor and exercise interventions designed to increase PA and reduce sedentary behaviour in patients on dialysis may improve health related outcomes and be cost effective in the longer term. However, there remains a pressing need for high-quality grade A evidence from randomised controlled trials in order to evaluate the clinical benefit and cost effectiveness of intradialytic exercise. It has been suggested also that a rigorously designed, and appropriately powered pragmatic, RCT study may also go some way towards addressing the issue of whether physical inactivity contributes to increased mortality in these patients or is just an indicator of poor general condition that increases mortality risk (27). The importance of this question can only increase in view of the rising prevalence of CKD.

2. Study Objectives and Design

2.1 Study Objectives

2.1.1 Primary Objective

To determine, in comparison to usual care, whether usual care augmented by intradialytic exercise training improves health-related quality of life in stage 5 CKD patients receiving maintenance haemodialysis renal replacement therapy

2.1.2 Secondary Objectives

- To determine, in comparison to usual care, whether usual care augmented by intra-dialytic exercise training improves the physical function of stage 5 CKD patients receiving maintenance haemodialysis renal replacement therapy
- ii. To compare the effect of usual care augmented intra-dialytic exercise training versus usual care on systemic and biochemical markers of vascular and cardio-metabolic health of stage 5 CKD patients receiving maintenance haemodialysis renal replacement therapy
- To assess, in comparison to usual care, whether usual care augmented by intra-dialytic exercise training is associated with an excess of adverse events in stage 5 CKD patients receiving maintenance haemodialysis renal replacement therapy

- iv. To explore and document the views of participants and members of the renal care teams in relation to their experiences of usual care and intra-dialytic exercise-augmented usual care
- v. To estimate the cost-effectiveness of augmenting, with intra-dialytic exercise training, the usual care stage of 5 CKD patients receiving maintenance haemodialysis renal replacement therapy

2.1.3 Primary Endpoint

The primary endpoint for this study will be the documented change in Kidney Disease QOL questionnaire Physical Composite Score (KDQOL-PCS) between baseline and 6 months. The KDQOL is a disease-specific quality of life measure.

2.1.4 Secondary Endpoint

Assessed at 6, 9 and 15 months. Change between baseline and follow-up for:

- KDQOL-PCS
- KDQOL-MCS
- KDQOL-Vitality subscale
- KDQOL- symptom burden subscale
- IPAQ
- Height (at screening visit only), Weight and anthropometric (BMI, waist to hip ratio)
- Peak aerobic capacity
- Duke Activity Status Index (self-report 12-item activity of daily living questionnaire)
- 10m Timed-up-and-go (composite test of leg strength, balance, coordination and gait speed)
- Sit-to-stand 60 (proxy measure of lower extremity muscular endurance)
- Tinetti Falls Efficacy Scale
- Habitual physical activity (a self-report assessment via International Physical Activity Questionnaire)
- Habitual physical activity (GT3X tri-axial accelerometer)
- Arterial stiffness (via pulse wave velocity and augmentation index)
- Blood pressure
- Hb
- ESAs
- Phosphate
- Parathyroid hormone (PTH)
- EQ-5D, a generic multi-attribute health related QOL questionnaire for use in cost utility analysis.
- Health Economic questionnaire regarding resource use
- All hospitalisations
- All-cause mortality
- Cardiovascular mortality
- Safety / Harms (SAE)

Qualitative Study and analysis

A constructivist phenomenological approach will be used to learn about views and perceptions of participants and build greater understanding of varied perspectives of both service users and providers (Crotty 1998; Grbich 1999). Focus groups and individual interviews will be used as most appropriate to the stage of the study and location of data collection. All participants in the pilot study and RCT will be eligible for inclusion in the qualitative sub-study. Purposive sampling will be used to ensure varied experiences and viewpoints are represented, for example, including service users and providers from different study regions, including people in both study arms, and aiming to include people with different participation rates and response to the intervention. Appropriate topic guides will be developed for pilot study and RCT, and for service users and providers; questions will be discussed within the project team and steering group.

Health Economic analysis

To maximise relevance to policy, the health economic evaluation will follow the quidelines recommended by NICE, including the use of cost-utility analysis and adopting an NHS costing perspective. Quality adjusted life years (QALYs) will be derived from utility scores generated using a standard UK algorithm from the EQ-5D. Resource use associated with physiotherapy assistant time and [training in use of equipment and delivery of personal exercise programmes per patient] time will be recorded prospectively using timesheets for the intervention group. Equipment costs will be calculated using the annuity method with discounting rates set as per NICE base case]. Other health care resource use will be captured through patient questionnaires administered monthly during dialysis sessions. Factors to be measured have been extracted from the literature and consultation with experts and include (but are not limited to): primary care consultations, nephrologists consultations, calls to NHS Direct/NHS24, accident and emergency visits, NHS provided devices and aids and Physiotherapy sessions. During the internal pilot phase a free format "other" category will be included to check for omitted items. Additionally, hospital admissions and medication use will be recorded (with consent) from nephrologists' records. Resource use estimates will then be combined with standard UK sources to estimate total NHS costs.

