4.5.2 Planned Intervention: Intra-dialytic Exercise Training

The intra-dialytic exercise prescription will be based on current Physical Activity (PA) guidelines for the elderly (28) and for people with diabetes (29) and cardiovascular disease (30). These recommend a minimum target amount of 1000 kcal per week be expended in PA for health benefits with optimal benefits associated with weekly target PA accumulation of 1500 to 2000 kcal. As opportunity for structured prescribed exercise is largely restricted to patients' three haemodialysis days the eventual aim is for the patients to accumulate as great a proportion of this minimum threshold level of 1000 kcal per week via intra-dialytic exercise. Peak aerobic capacity assessment will be conducted to derive and individualise the exercise prescription. Using a modified cycle ergometer, aerobic exercise will be performed in a semi-recumbent position, 3 times per week during the first two hours of haemodialysis. The initial prescription will be set in the moderate intensity range of 40-60% of peak aerobic capacity, progressing to 75% level by the end of the intervention. This exercise adoption phase aims to support patients in achieving the "average" target daily PA level within each intra-dialytic exercise session (21 minutes, continuous cycling, moderate intensity range or ~140 kcal/cycling session) and approximating 42% of the minimum weekly PA target. The exercise prescription will be individually increased through three additional phases of progression (months 2-4), behaviour development (months 5-6); and maintenance (months 7-9). The aim is for patients to increase exercise duration and intensity to expend around 185, 230, and 250 kcal per intra-dialytic exercise session respectively in each phase. Exercise duration and intensity will be regularly adjusted via ratings of perceived exertion, to ensure that the planned initial target volume of exercise (kcal per week) is "achieved" by all patients. These energy expenditure goals are deliverable via an increase in intra-dialytic cycling from 21 to 40 minutes, at moderate/vigorous exercise intensity, and will result in 55%, 69% and 75% respectively, of target weekly minimum PA volume being achieved. Twice per week, patients will also complete lower extremity muscular conditioning exercise, using ankle weights, after the aerobic cycling exercise. Drop-out rates for similar exercise training studies ranges from 17% to 25% (23) however all patients enrolled in the trial will be followed up to allow an intention to treat analysis.

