1.0 Aim

To establish the accuracy of the self-reported long form International Physical Activity Questionnaire (IPAQ) in estimating the type and quantity of Physical activity (PA) levels as well as time spent in sedentary activities vs. objectively measured PA data and sedentary time using GT3X accelerometers.

The IPAQ is a validated questionnaire across a range of ages and populations with different demographical/clinical characteristics (Strath et al. 2013), but its validity against objectively recorded PA data has not been reported in patients with CKD. The IPAQ is concerned with type and amount of PA performed over a short recall-period of the previous 7 days. Although, a range of short recall PA questionnaires have been used in the CKD population to characterise PA behaviour, none have been validated against objectively measured data and thus no best recommendations exist on a PA assessment tool. This area of research is still very much under active development and therefore, this sub-study can significantly contribute to extremely limited literature about the clinical and research accuracy of this tool to characterise PA behaviour vs. uni-axial and tri-axial derived accelerometry and inclinometry as captured by the GT3X device.

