2.0 Additional data to be recorded

Uni-axial and tri-axial based accelerations over 7 days will be recorded in order to establish the level of agreement between the IPAQ-LS derived data and GT3X recorded data.

Comparison outcomes will include the following, plus any other deemed necessary upon examination of data;

- i) Total time (min) per week in walking
- ii) Total time (min) per week in moderate intensity activities
- iii) Total time (min) week in low intensity activities
- iv) Total time (min) per week in vigorous activities
- v) Total time (min) per week in all activities
- vi) Classification of PA behaviour as meeting or not meeting existing PA guidelines (>150 min/week at moderate intensity)
- vii) Total time (min) per week in sedentary activities

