3.0 Sub-study procedures

The patient assessment procedure for the sub-study is as per main PEDAL study GTX3 Accelerometer assessment.

Patients will be required to complete the IPAQ questionnaire upon return of the GT3X device, and not on the day that the GT3X device will be given to the patient, so that data reported on IPAQ reflects PA data recorded by the GT3X device over the previous 7 days

Data will be reported and analysed using records which will be separate to the eCRF.

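### At 6 months, and possibly at 9 months, the endpoints labelled habitual physical activity are taken over a week that includes the prescribed cycling in the exercise arm only

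*Protocol*

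**What the plan says.** Section 2.1.4 of the protocol names two endpoints with the same label, "Habitual physical activity (a self-report assessment via International Physical Activity Questionnaire" and "Habitual physical activity (GT3X tri-axial accelerometer". Both are assessed as change from baseline at 6, 9 and 15 months. The Secondary Outcomes paragraph of section 6 analyses continuous secondary outcomes in the same way as the primary, that is, with adjustment for baseline.

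Both instruments look at one week. Appendix 1 gives the GT3X 7 days. Appendix 3 says "The IPAQ is concerned with type and amount of PA performed over a short recall-period of the previous 7 days" and "Uni-axial and tri-axial based accelerations over 7 days will be recorded". It aligns the two: "Patients will be required to complete the IPAQ questionnaire upon return of the GT3X device". It also ties this to the main trial: "The patient assessment procedure for the sub-study is as per main PEDAL study GTX3 Accelerometer assessment".

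Section 4.5.2 prescribes cycling in EXHD three times a week during dialysis. The energy target per session rises from about 140 kcal to 185, 230 and 250 kcal over the later phases. Section 2.2 places the 9-month visit at the end of the intervention and the 15-month visit 6 months after it. Table 2 (section 4.6) allows 1 week either side of each visit.

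The protocol does not restrict either endpoint to time off dialysis, and it does not tell participants how to report the sessions on IPAQ.

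**The concern.** Habitual activity suggests what patients do in their ordinary lives. Section 1.1 hopes that the programme may lead patients to keep up a more active life in the longer term, and a reader would take these endpoints as evidence on that question. If the measured week contains the allocated treatment in one arm only, a positive difference may record attendance at supervised sessions. A total for the week could also hide a fall in activity away from dialysis. Adjustment for baseline does not help, because neither arm was cycling at baseline: assessment precedes randomisation (section 2.2), and patients are naive to intra-dialytic exercise (section 4.1).

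**Working it through.** **Inputs.** Section 4.5.2: 3 sessions per week; 140, 185, 230 and 250 kcal per session by phase; weekly minimum 1000 kcal; months 5-6 are the 230 kcal phase and months 7-9 the 250 kcal phase. Section 1.1: 9 months of intervention. Table 2: visits within 1 week of the due date. Appendices 1 and 3: a 7-day window.

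**Step 1: reproduce the plan's own percentages.** Share = 3 × kcal per session ÷ 1000.

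- 3 × 140 = 420, or 42.0% (stated 42%)
- 3 × 185 = 555, or 55.5% (stated 55%)
- 3 × 230 = 690, or 69.0% (stated 69%)
- 3 × 250 = 750, or 75.0% (stated 75%)

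All four agree, apart from rounding down in the second. The protocol therefore counts the prescribed cycling as physical activity. The two shares that matter for the assessments on treatment are 69% and 75%.

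**Step 2: place the measurement week.**

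- *6 months.* With the visit up to 1 week early or late, and the 7 days either before or after it, the recorded week lies within 2 weeks of month 6. The programme runs to month 9, so the whole week is inside it. With dialysis usually three times a week, it spans about three prescribed sessions in EXHD.
- *9 months.* The visit marks the end of the intervention. If the device is handed out at the visit, the week may follow the last session. If it is worn beforehand, the week may precede or straddle that session. The protocol does not say which.
- *15 months.* The intervention has been over for 6 months. Neither arm has trial sessions in the week.

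**Step 3: what the comparison contains.** Suppose the cycling adds to other activity. This is plausible, because section 1.2 describes dialysis as the most inactive time for these patients. Then

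measured difference = difference outside dialysis + a × c × W,

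where W is the prescribed weekly cycling, a the adherence and c the proportion that the instrument captures. The documents give neither a nor c. With no true difference outside dialysis, W = 690 kcal and c = 1 (an assumption):

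- a = 1.0: 690 kcal/week
- a = 0.75: 0.75 × 690 = 517.5 kcal/week
- a = 0.5: 0.5 × 690 = 345 kcal/week

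With W = 750 the figures are 750, 562.5 and 375. With c = 0 they are all zero. The possible contribution therefore runs from nothing to 690 or 750 kcal/week. The protocol gives no standard deviation for IPAQ or GT3X, so the effect on a test cannot be calculated.

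**The case against.** Wear rules, accelerometer processing and IPAQ scoring are often left to a SAP or to operating procedures; section 3.1 mentions a procedure for outcome assessments. Total weekly activity is also a legitimate outcome. Section 1.2 presents exercise during dialysis as a direct answer to prolonged inactivity, and section 4.5.2 counts it towards the weekly target. These are two of many secondary endpoints, and no secondary objective in section 2.1.2 names physical activity.

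Much of this stands, and it keeps the point minor. It does not remove it. What participants are told about IPAQ, and whether dialysis times are recorded for the wear week, must be settled when the data are collected. Self-reported minutes that were mixed at source cannot be cleanly separated later. If total activity is what is meant, habitual is the wrong label.

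A reader might infer more than the documents support:

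- *That three sessions are certainly included at 9 months.* The timing of the wear week is not fixed.
- *That the cycling is 42% to 80% of a 150 min/week threshold, from 3 × 21 = 63 and 3 × 40 = 120 minutes.* The 21 minutes belong to the initial phase, and the minutes at month 6 are not stated. The criterion "Classification of PA behaviour as meeting or not meeting existing PA guidelines (>150 min/week at moderate intensity" belongs to the validity sub-study in Appendix 3, not to the between-arm endpoint. It refers to moderate intensity, whereas the prescription reaches moderate to vigorous.
- *That IPAQ scoring necessarily counts the sessions.* No scoring rule is given. Nor is it stated whether the GT3X is worn on dialysis or registers semi-recumbent cycling.

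**Conclusion.** The point holds firmly at 6 months and conditionally at 9 months. As written, the habitual-activity endpoints can show a between-arm difference that partly reflects session attendance. At full adherence the prescribed cycling amounts to 69% (months 5-6) or 75% (months 7-9) of the 1000 kcal weekly minimum. The part that reaches the endpoint depends on adherence and on capture by each instrument, so its size is unknown.

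It would be wrong to conclude that the 15-month result is distorted. The between-arm comparison there is clean, and it is the visit that bears on lasting change. Only a fall from the 6- or 9-month values to 15 months could be partly artificial. The primary endpoint, KDQOL-PCS at 6 months, is not affected.

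**What to change.** Define the habitual-activity endpoint as activity outside dialysis sessions, and apply the definition identically in both arms:

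- GT3X: exclude data between the recorded dialysis start and stop times in the wear week.
- IPAQ: instruct participants to leave out activity during dialysis. Do not subtract logged session minutes afterwards. That would alter EXHD only and over-correct wherever the sessions were never reported. Section 4.5.2 also does not say that the physiotherapy assistants log minutes; it mentions prescription milestones and compliance.
- Report total GT3X activity, including dialysis time, as a supporting result.
- State whether the 9-month wear week falls before or after the last session.

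The cost is small: dialysis times for the wear week, one line of IPAQ instruction and one extra derived variable. The difference at 6 months may be smaller as a result.
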